4.3.2.2 Presentation

AEs will be presented for actual treatment for the Safety Analysis Set in categories as below.

- AEs
- SAEs
- AEs with outcome death
- AEs leading to IMP discontinuation
- AEs leading to study discontinuation
- AESIs
- Related AEs
- Related SAEs
- Related AESIs
- Grade 3 or higher AEs
- Grade 3 or higher AESIs
- Related Grade 3 or higher AEs
- Related Grade 3 or higher AESIs

Summaries will include the number and percentage of participants reporting at least one event, and exposure adjusted rates, where appropriate.

An overview table of AEs will be presented for actual treatment, including the number and percentage of participants for each category.

Moreover, each category will be presented by SOC and PT. Specifically, for AESI summaries these will be presented by the AESI category and PT. For Grade 3 or higher summaries, a breakdown of participants with grades ≥ 3 , 3, 4 and 5 will be presented for each PT (taking the worst grading if a participant experiences multiple events within a PT). Should a participant experience multiple events within a category, the participant will be counted only once for that category.

Summaries of the most common AEs (occurring in $>1\%$, and $>5\%$ of participants in any treatment group) will be presented by PT. SAEs causing discontinuation of the study treatment and SAEs causing discontinuation from the study will also be summarized by PT.

AEs will be summarized by maximum intensity. If a participant reports multiple occurrences of the same AE within the same study period, the maximum intensity will be taken as the highest recorded maximum intensity (the order being mild, moderate, severe, potentially life-threatening, and fatal).

In addition, participants with adjudicated cardiovascular events will be summarized by the following categories and overall:

- Cardiac ischemia
- Cardiovascular death
- Heart failure
- Stroke
- Thrombotic Event

Summary statistics will be presented for time to onset for adjudicated cardiovascular events, calculated as (Date of Onset) – (Date of first IMP Dose) + 1. Date of Onset is defined as the start date of the adverse event or laboratory assessment that leads to adjudication.

The number and percentage of participants assessed for adjudication will be presented with categories for confirmed and unconfirmed.

Serious adverse events with a preferred term identified by the standardized MedDRA query (SMQ) for embolic and thrombotic events (Appendix A 4) will be summarized by SOC and PT. Furthermore, a separate summary of serious adverse events for those identified by the same SMQ or with SOC of cardiac disorders will be presented by SOC and PT.

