8.3.5 Adverse Events Based on Signs and Symptoms

All AEs spontaneously reported by the participant or care provider or reported in response to the open question from the study site staff: ‘Have you/the child had any health problems since the previous visit/you were last asked?’ or revealed by observation will be collected and recorded in the eCRF. When collecting AEs, the recording of diagnoses is preferred (when possible) to recording a list of signs and symptoms. However, if a diagnosis is known and there are other signs or symptoms that are not generally part of the diagnosis, the diagnosis and each sign or symptom will be recorded separately.

Diagnoses of suspected or confirmed COVID-19, confirmed asymptomatic SARS-CoV-2 infection, and/or recurrence of COVID-19 (or of SARS-CoV-2 reinfection) will be collected and recorded in the eCRF as an AE. Additionally, if a participant has prolonged COVID-19 for approximately 3 months, then an AE of post-acute COVID (“long COVID”) will be recorded in the eCRF as an AE (In the case of post-COVID, symptoms may be of new onset following initial recovery from an acute COVID-19 episode, persist from the initial illness, or fluctuate/relapse over time; [WHO 2021](#)).

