Other: Study design	20Nov2023	Study is early terminated. Participants remained in the study are to complete final assessments at least 6 months after their final dose of AZD7442. No additional dose of AZD7442 will be given.	Yes	On 30 March 2023, the FDA requested that the Sponsor halt further dosing for the ENDURE Study, given that AZD7442 (EVUSHELD) is not active against > 99% of the currently circulating SARS-CoV-2 variants in the USA, the benefit risk assessment may not be favorable. After consideration of the FDAs request, the Sponsor has decided to terminate this study.
Other: Changes to CSP planned analysis	20Nov2023	Additional section added to explain the analysis set definition.	N/A	Clarify the participant inclusion / exclusion and participant visit inclusion / exclusion differences in the analysis set definition.
Other: Timing of the analyses	20Nov2023	Remove interim analysis and only final analysis is planned for the study	Yes	Due to study design change, only final analysis is needed.
Other: NLF PK analysis set	20Nov2023	Addition of NLF PK analysis set	N/A	Clarify NLF PK concentration analysis set
Other: Visit Window	20Nov2023	Remove Day 1 pre-dose time point from the visit window for Serum and NLF PK parameters.	N/A	
Other: Protocol deviation category	20Nov2023	Align protocol deviation categories with PDMP	N/A	Protocol deviation monitoring plan (PDMP) is updated, this change is to align SAP with the PDMP.
Data presentations	20Nov2023	Remove Region from the subgroup presentation	N/A	Only participants in US is enrolled.
Other: Partial date imputation	20Nov2023	Addition of partial COVID-19 vaccination date imputation method	N/A	Method to impute incomplete date that was collected for statistical analysis.
Data presentations	20Nov2023	Concomitant medication summaries will use ATC level 4 instead of level 2	N/A	To display more specific drug category

Statistical analysis method	20Nov2023	Further clarify the correlation calculation method using mixed model for repeated measurements and bootstrapping.	N/A	Clarify the statistical method used for calculation of nAb and PK concentration correlation.
Data presentations	20Nov2023	Clarify 2 assays are used for nAb titers	N/A	Two assays: one for SARS-CoV-2 authentic virus and the other pseudovirus nAb are both collected.

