4.2 Endpoint Analyses

This section covers details related to the endpoint analyses such as primary, secondary, other endpoints.

Statistical category	Endpoint	Population	Intercurrent event strategy	Population level summary (analysis)	Details in section
Objective 1: To evaluate the safety, and tolerability of AZD7442 in adult and pediatric participant ≥ 12 years of age.					
Primary	Incidence and exposure adjusted incidence of AEs, SAEs, and AESIs	Safety analysis set	N/A	Descriptive	Section 4.3.2
Objective 2: To evaluate the immunogenicity of AZD7442 in adult and pediatric participant ≥ 12 years of age.					
Primary	Incidence of ADA to AZD7442	ADA evaluable analysis set	N/A	Descriptive	Section 4.2.1
Objective 3: To evaluate the PK of AZD7442 in adult and pediatric participant ≥ 12 years of age.					

Secondary	Serum AZD7442 (tixagevimab and cilgavimab) concentrations PK parameters	PK analysis set	N/A	Descriptive	Section 4.2.24.2.1
Objective 4: To determine anti-SARS-CoV-2 nAb levels in serum after administration of AZD7442 in adult and pediatric participant ≥ 12 years of age.					
Secondary	Changes from baseline in GMTs and GMFRs values in SARS-CoV-2 nAbs (wild-type assay or pseudo neutralization assay)	nAb evaluable analysis sets	N/A	Descriptive	Section 4.2.2
Objective 5: Exploratory – See Section 4.2.3					

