4.3.2 Adverse Events

4.3.2.1 Definitions and Derivations

All Adverse events (AEs) will be coded using the MedDRA dictionary, version 25.0 or higher.

The safety of AZD7442 will be assessed by:

- Incidence of AEs
- Incidence of Serious Adverse Events (SAEs)
- Incidence of adverse events of special interest (AESIs)

AEs and SAEs

AEs will be recorded from the time of the first IMP administration throughout the study up to and including the last visit. SAEs are those events recorded as “Serious” on the AE page of the eCRF. SAEs will be recorded from the time of signing the informed consent form. The definition of AEs and SAEs can be found in Protocol Appendix B.

Listings of AEs and SAEs will be provided. Events prior to the first dose of IMP will only be presented in the listings. For events with partial dates, if the known part of the date indicates that the event stopped before the first dose of IMP, it will be considered as an event prior to the first dose of IMP. Otherwise, it will be considered as an event post first dose of IMP.

AESIs

AESIs are events of scientific and medical interest, specific to the further understanding of the IMP safety profile, and require close monitoring and rapid communication by the investigators to the Sponsor. An AESI can be serious or non-serious. All AESIs will be recorded in the eCRF. AESIs for AZD7442 include the following:

- Anaphylaxis and other serious hypersensitivity reactions, including confirmed diagnosis of immune complex disease
- Injection site reactions (IM administration) and infusion-related reactions (IV administration)
- Cardiovascular and thromboembolic events
- Multisystem inflammatory syndrome – pediatric participants

Deaths

If any participants die during the study as recorded on the “Death Details” page of the eCRF, the number and percentage of participants with death related to COVID-19 and those with other deaths will be summarized by actual treatment group based on the Safety Analysis Set.

Severity

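### COVID-19 counts as an adverse event, but the SAP plans no AE, SAE or Grade 3+ summary that leaves it out

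*SAP*

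**What the plan says.** Protocol 8.3.5 lists "Diagnoses of suspected or confirmed COVID-19, confirmed asymptomatic SARS-CoV-2 infection, and/or recurrence of COVID-19" and ends that list with "reinfection) will be collected and recorded in the eCRF as an AE". It adds long COVID as a further AE, and Protocol 8.1.1 gives the same instruction.

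SAP 4.2 defines the primary safety endpoint as "Incidence and exposure adjusted incidence of AEs, SAEs, and AESIs". It is summarized descriptively in the Safety Analysis Set, with the intercurrent event strategy marked not applicable. SAP 4.3.2.2 lists 13 AE categories and says: "An overview table of AEs will be presented for actual treatment, including the number and percentage of participants for each category". It continues: "Moreover, each category will be presented by SOC and PT". In SAP 4.3.2.1 the numerator of the exposure-adjusted rate is the participants with an AE in the category, with no exclusion by cause.

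Deaths are the exception. There, "the number and percentage of participants with death related to COVID-19 and those with other deaths will be summarized" by actual treatment group.

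The SAP amendment history records why dosing stopped: AZD7442 was "not active against > 99% of the currently circulating SARS-CoV-2 variants in the USA".

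**The concern.** The same illness is an exploratory efficacy outcome (SAP 4.2.3.4.1) and an event in the primary safety summaries. Someone reading the any-AE, any-SAE or any Grade 3+ row by arm will take it as a statement about tolerability. Part of that row is infection, which depends on protection and on the virus circulating during follow-up.

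Follow-up can also differ by arm. Day 274 is a dosing day only in Arm A. Under the termination rules in Protocol 1.3, a last dose on Day 183 leads to early discontinuation in place of Day 365, and a last dose on Day 274 to early discontinuation in place of Day 456. Some Arm A participants could therefore be followed 456 − 365 = 91 days longer, in a period when the product may have been inactive. Dividing by participant-years allows for the extra time but not for a change in infection pressure.

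Protocol 4.3 says the data are to inform dose level and dosing interval, so the two columns will be read against each other even though nothing is tested.

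**Working it through.** **The plan's own figure.** Protocol 9.2 and SAP 1.3 give a 95% chance of at least one AE in 100 participants at a 3% rate. 1 − 0.97^100 = 0.952, so it reproduces. Nothing below changes it.

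**Which rows are exposed.** Of the 13 categories, four are AESI rows. COVID-19 is not an AESI (Protocol 8.3.4); only pediatric multisystem inflammatory syndrome is defined by infection. Three more are Related AE, Related SAE and Related Grade 3+ AE. Protocol Appendix B 3 directs that cases due to lack of effect be judged not related, so these should hold little COVID-19. Six all-cause rows remain. Three of them carry the headline: AEs, SAEs, and Grade 3 or higher AEs.

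**Size.** Let b be the risk of a non-COVID event, equal in both arms, and c_A and c_B the arms' risks of a COVID-19 event in that category, independent of other events.

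- Row risk = 1 − (1 − b)(1 − c)
- Arm difference = (1 − b)(c_B − c_A)

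The documents give no value for b or c. All inputs below are assumptions, and the arm labels could be swapped.

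| Row | b | c, one arm vs other | Row reads | Difference (points) |
|---|---|---|---|---|
| Any AE | 50% | 10% vs 20% | 55% vs 60% | 5 |
| Any AE | 50% | 10% vs 30% | 55% vs 65% | 10 |
| Any AE | 70% | 10% vs 20% | 73% vs 76% | 3 |
| Any AE | 70% | 20% vs 40% | 76% vs 82% | 6 |
| Any AE | 90% | 10% vs 20% | 91% vs 92% | 1 |
| Any AE | 90% | 20% vs 40% | 92% vs 94% | 2 |
| SAE or Grade 3+ | 5% | 2% vs 8% | 6.9% vs 12.6% | 5.7 (ratio 1.83) |
| SAE or Grade 3+ | 10% | 1% vs 5% | 10.9% vs 14.5% | 3.6 (ratio 1.33) |
| SAE or Grade 3+ | 20% | 1% vs 3% | 20.8% vs 22.4% | 1.6 (ratio 1.08) |

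If c_A = c_B the difference is zero and only the level of the row rises. At b = 70% and c = 10% in both arms, each arm reads 73%. A row excluding COVID-19 would read b in both arms throughout.

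**Can the count be recovered from planned tables?** Take the 76% vs 82% case with 100 per arm. The tables would show 76 with any AE and 20 with COVID-19 in one arm, and 82 and 40 in the other. The number with a non-COVID AE lies between 76 − 20 = 56 and 76 in the first arm, and between 82 − 40 = 42 and 82 in the second. The true value is 70 in both, but the tables cannot show it, because participants with both kinds of event are counted once. With several COVID-19 preferred terms, even the number with any of them cannot be read off.

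**Do the efficacy tables supply it?** No. SAP 4.2.3.4.1 uses the FAS, requires an RT-PCR-confirmed symptomatic case (or COVID-19 hospitalization or death), and censors at vaccination, restricted medication and certain deviations. The AE count uses the Safety Analysis Set, includes suspected and asymptomatic cases, and has no censoring.

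**The case against.** The strongest reply has four parts.

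- **COVID-19 belongs in these rows.** An AE counts regardless of cause (Protocol Appendix B 1), and antibody-dependent enhancement is a named potential risk (Protocol 2.3.1). This stands: the all-cause rows must stay.
- **The arms may not differ in infection.** Both receive the same product, 1:1, and Protocol 4.3 describes similar overall exposure. Loss of variant activity would push infection rates together. This stands as a reason to expect a small effect. It does not make equal risk certain, since timing and follow-up can differ.
- **The shift is within noise.** With 100 per arm, the standard error of 76% vs 82% is √(0.76×0.24/100 + 0.82×0.18/100) = 5.7 points, so a 6-point shift is about one standard error. For 11.8% vs 14.5% (b = 10%, c = 2% vs 5%) the standard error is 4.8 points and the shift of 2.7 is about 0.6 of it. No hypothesis is tested. This stands, and it limits the importance of the point.
- **The information is partly there.** COVID-19 terms appear in the SOC/PT tables, deaths are split, and AE listings would let someone derive the count. The listings could be used that way, but the terms would be chosen after seeing the data, and a reader with only the tables could not do it.

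A reader might go further and infer that every headline row is affected, or that the safety comparison measures lost prophylactic effect. The documents support neither. Seven of the 13 categories are largely untouched. There is no placebo arm and no planned pooled AE column, so the rows can absorb only a difference between two active regimens or the background infection level.

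**Conclusion.** The point holds as a reporting gap in three descriptive rows (all-cause AEs, SAEs, and Grade 3 or higher AEs) and their exposure-adjusted rates. No planned output gives the participant count without COVID-19. The SAP already makes a comparable separation elsewhere: it splits deaths, and it excludes post-infection neutralizing-antibody data from the main-visit summaries (SAP 4.2.2.4.2).

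Size and direction are unknown. The ranges of 1 to 10 points for any AE and 1.6 to 5.7 points for SAE or Grade 3+ rest on assumed, unequal COVID-19 risks, equal background risk and independence. The any-AE effect shrinks as background AEs become more common; in relative terms the SAE and Grade 3+ rows are the more sensitive. This is a cheap improvement to interpretation. It does not show that the planned rows are wrong or that the arms will differ.

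**What to change.** Leave the all-cause rows as they are. In SAP 4.3.2.2, add three supplementary rows to the overview table, and to the exposure-adjusted rates: any AE, any SAE, and any Grade 3 or higher AE, each excluding COVID-19 terms.

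Fix the preferred-term list before database lock. It should cover COVID-19, suspected COVID-19, asymptomatic infection, reinfection and post-acute COVID-19, plus COVID-19 pneumonia and any other term coded as a COVID-19 manifestation. Protocol 8.1.2 characterizes severe COVID-19 by pneumonia or hypoxemia, so a list without such terms would leave the worst cases in the SAE and Grade 3+ rows.

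The cost is three more rows in the overview table and a short term-list review by the medical and statistical team. No new data and no change to the sample size are needed.

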4.3.3 Clinical Laboratory, Blood Sample and Urinalysis

4.3.3.1 Definitions and Derivations

Hematology, serum clinical chemistry, coagulation, cardiac biomarker, and urinalysis will be performed as per the schedule of events (refer to Protocol Sections 1.3 and 8.2.4 for

schedule and lists of parameters). A urine pregnancy test will be performed at screening and per the schedule of events (refer to Protocol, Section 1.3). If urine tests positive or indeterminate, a serum test will be performed for confirmation.

Quantitative laboratory parameters reported as “< X”, i.e. below the lower limit of quantification (BLQ) or “> X”, i.e. above the ULOQ, will be converted to X for the purpose of quantitative summaries, but will be presented as recorded, i.e. as “< X” or “> X” in the listings.

Quantitative laboratory parameters will be compared with the relevant central laboratory normal ranges in SI units and categorized as:

- Low: Below the lower limit of the laboratory normal range.
- Normal: Within the laboratory normal range (upper and lower limit included).
- High: Above the upper limit of the laboratory normal range.

Quantitative laboratory parameters with available Common Terminology Criteria for Adverse Events (CTCAE) toxicity grades will be categorized as follows where higher grades representing a more severe toxicity (refer to Appendix [A 2](#)) for each parameter toxicity grade criteria):

- Grade 1 (i.e., mild);
- Grade 2 (i.e., moderate);
- Grade 3 (i.e., severe);
- Grade 4 (i.e., life-threatening);
- Grade 5 (i.e., death).

Although not defined in the CTCAE toxicity grading system, version 5, non-missing laboratory parameter results not meeting any of the 5 grades defined in the CTCAE toxicity grading system will be categorized as ‘No Event’ for the purpose of the shift from baseline summaries.

4.3.3.2 Presentations

The following summaries will be provided by actual treatment group for laboratory parameters:

- Observed and change from baseline in Standard International (SI) units by visit (for quantitative parameters).
- Observed and change from baseline for Illness Visits as defined in Section [3.3.1](#) (for coagulation parameters) in SI units by Illness Visit (the Illness Visits where the

series corresponds to positive RT-PCR test, as defined in Section 4.2.3.4.1, will be used in the summary).

- Number and percentage of participants in each laboratory parameter category by visit (for categorical parameters).
- Maximum post-baseline ALT/AST observed value categorized as $< 3 \times$ upper limit of normal (ULN), ≥ 3 to $< 5 \times$ ULN, ≥ 5 to $< 10 \times$ ULN or ≥ 10 ULN by maximum post-baseline total bilirubin (TBL) observed value categorized as $< 2 \times$ ULN or $\geq 2 \times$ ULN.
- Heatmap of the maximum post-baseline observed value in ALT value by the maximum post-baseline observed value in TBL value, both expressed as multiple of ULN.
- Heatmap of the maximum post-baseline observed value in AST value by the maximum post-baseline observed value in TBL value, both expressed as multiple of ULN.
- A listing of participants with at least one observed value in ALT value $\geq 3 \times$ ULN, AST value $\geq 3 \times$ ULN or TBL value $\geq 2 \times$ ULN will be provided.
- Listing of participants with at least one abnormal laboratory observed value outside the normal range criteria (refer to Section 4.3.3.1).

The following further summaries may be provided by actual treatment group for laboratory parameters:

- Shift from baseline to the worst post-baseline observed value according to the CTCAE toxicity grades (for quantitative parameters with available CTCAE toxicity grades; refer to Section 4.3.3.1).
- Shift from baseline to the maximum/minimum post-baseline observed value according to normal range criteria (for quantitative parameters without available CTCAE toxicity grades; refer to Section 4.3.3.1).

4.3.4 Vital Signs

4.3.4.1 Definitions and Derivations

Vital signs will be performed at time points specified in Protocol Section 1.3, including the following parameters:

- Systolic blood pressure (SBP) (mmHg)
- Diastolic blood pressure (DBP) (mmHg)
- Pulse rate (beats per minute [bpm])

- Body temperature (C)
- Respiratory rate (breaths/min)
- Oxygen saturation (%)

4.3.4.2 Presentations

For severity grades of abnormal Vital Signs refer to Appendix [A 3](#).

The following summaries will be provided by actual treatment group for each vital sign parameter:

- Observed and change from baseline by visit
- Observed and change from baseline for Illness Visits (as defined in Section [3.3.1](#)) by Illness Visit (the illness visits where the series corresponds to positive RT-PCR test, as defined in Section [4.2.3.4.1](#), will be used in the summary).
- Number and percentages of participants with at least one abnormal post-baseline observed value (refer to Appendix [A 3](#))
 - Participants will be summarized by the worst severity observed.

All vital sign data will be listed. Indicators will be included for illness visits to distinguish those with positive RT-PCR results from those with negative RT-PCR results.

4.3.5 Electrocardiogram

4.3.5.1 Definitions and Derivations

The following ECG parameters will be measured for this study as per the schedule of events (see Protocol Section 1.3):

- PR interval (msec)
- QRS duration (msec)
- QT interval (msec)
- QTc interval (msec)
- QTcB interval (msec)
- QTcF interval (msec)
- RR interval (msec)
- ECG mean heart rate (beats/min)

The overall interpretation of the ECG results will be classified as normal, abnormal not clinically significant, or clinically significant abnormal by the investigator.

Additionally, markedly abnormal quantitative ECG parameters will be identified in accordance with the following predefined markedly abnormal criteria:

- Observed values for QTc, QTcF, and QTcB intervals will be classified as:
 - > 450
 - > 480
 - > 500 msec
- Change from baseline for QTc, QTcF, and QTcB intervals will be classified as:
 - > 30 msec increase from baseline
 - > 60 msec increase from baseline

It is to be noted that the previous categories are not mutually exclusive, but cumulative. For example, if a participant's worst post-baseline QTc post-baseline observed value is 490 mmHg, then this participant will be reported once under QTc > 450 msec and once under QTc > 480 msec.

